## II. Specific Aims

We propose a randomized clinical trial with **primary aims** to evaluate the: **1)** use, **2)** consequences (on cessation), and **3)** mechanisms of varenicline sampling. We will recruit between 648-660 smokers and randomize them to receive a 4-week sample of varenicline, NRT, or no sample, and will follow all for 6 months. Our remote focus derives from our hands-off (i.e., translatable) intent, yet our methods include both daily diary assessment and remote biological verification of smoking to enhance rigor. We are mindful of requirements for physician oversight and embed full precautions for safety. Our study sample will include smokers both wanting to quit and not (recruitment of each, with stratified randomization), which will allow for exploratory sensitivity analyses to assess the role of smoker motivation on outcomes.

In accordance with these Aims, we hypothesize that: 1) use of varenicline will be strong: >80% of study sample using medications on at least 50% of the sampling period; 2) relative to non-medication controls, sampling will result in higher incidence of quit attempts and biochemically verified cessation; 3) with greater changes in hypothesized mediators (motivation/confidence, decreases in treatment fatigue). Comparisons of varenicline vs NRT sampling a) uptake, b) mechanisms and c) outcomes are secondary but nonetheless compelling and offer additional significance, innovation, and rigor to our trial.

[figure not shown]
## III. Methods

Our three-fold objective is to determine 1) use, 2) consequences, and 3) mechanisms of varenicline sampling. We propose a three-group, randomized clinical trial in which adult smokers, recruited remotely across SC, inclusive of smokers wanting to quit and not, receive a 2-4 week sample of varenicline, combo NRT, or neither, to use as they wish. Remote, serial assessment of carbon monoxide will be used to verify smoking behavior. Uptake and use will be operationally defined as: a) use of medication (incidence, quantity, duration of use), b) conversion to independent use (i.e., obtaining a prescription for further use), and c) adverse events. We anticipate a side effect profile consistent with other trials of varenicline (some insomnia, nausea) but otherwise benign. Cessation-related outcomes include: a) use of additional quit resources (e.g., calls to quitline), b) quit attempts, and c) cessation (7-day point prevalence abstinence, CO verified). Mechanisms include measures of

motivation, confidence, knowledge of and attitudes toward medication, autonomy to quit, expectancies, and cessation fatigue. This is an expanded list from our earlier studies, which allows comparability to NRT sampling but also an opportunity to move forward. Whether and how these non-pharmacologic mechanisms differ for varenicline vs. NRT is an interesting question we can now address, though comparison of mediational models is not our primary focus. An overview of study design is shown in Figure 3.

### IIIa Important Design Issues

First, sending prescription medication through mail is not only acceptable, but common in clinical practice. We restrict our recruitment to South Carolina alone given medical oversight from our study physician. Since statewide tobacco policy is a constant (vs. nationwide heterogeneity), this is another advantage of keeping this within South Carolina. Second, we do not capture carbon monoxide levels at baseline (which would also allow us to verify baseline smoking status), and instead rely on self-report of smoking. We recognize this as a limitation, particularly if we wanted to examine levels of CO over time. To address this, we would have to separately send the CO monitor (before baseline assessment) and varenicline (after), which adds unnecessary complexity. CO is used to verify smoking status at follow-up, not to assess changes over time. Third, all participants receive a referral to the SC quitline, with rationale and benefits of use. We believe this is a minimum standard to provide for all smokers. Fourth, our design further extends our progression into technology-based remote assessment. This includes teleconsent, remote CO, and daily diaries during the sampling period. Consistent with translational intent for remote delivery, Week 0 contact will be via phone, but all subsequent follow-up will be online, with adequate precautions in place for safety monitoring. Fifth, our screening procedures now include methods to enhance sample diversity, to increase generalizability. For example, we can ensure that at least 30% of our sample is non-white, and at least 40% are of each gender. Other demographic minimums can be considered (e.g., income, education) if our initial sample is insufficiently representative.

### IIIb Participants

As before, we will recruit smokers statewide through various media outlets. Advertising will solicit smokers both motivated to quit and not; this will not be pitched as a treatment study. Smokers will be screened online for study eligibility, which includes innovative and automated methods to protect against duplicate entries, including those who might try to game (falsify) the criteria to gain study access. In our prior statewide sampling study, we recruited 157 participants in five months, in our ongoing trial of e-cigarettes, we've recruited 375+ in 15 months. Recruitment pace herein might be a bit slower given extra eligibility criteria. We are also excited by our newly developed procedures to ensure sample diversity. Online screening for our remote trials now includes methods to ensure at minimum 40% of each gender, and minimum 30% non-white participants. This is particularly important because a number of eligibility criteria are focused on technological reach (e.g., smartphone ownership), and **these new methods provide greater assurance of sample generalizability**.

- a) Eligibility will be contingent upon: 1) age 18+; 2) daily smoker (25+ days per previous month); 3) smoking 5+ cigarettes/day; 4) smoking  $\geq$  1yr; 5) has access to a medical provider who could write a prescription if needed; 6) not currently pregnant, breastfeeding, or planning to become pregnant (remote pregnancy testing is included within our ongoing proof-of-concept study of varenicline, and is working well); 7) no suicidal ideation in past month, nor any lifetime suicide attempt; 8) no current (past month) psychotic

### *IIIc Teleconsent, Baseline Assessment, & Randomization*

In our prior studies, recruitment from national sources was based on mail-based return of the consent form. That is, after determination of eligibility, we mailed a consent form (2 copies) and asked the participant to sign one copy and return to us in a pre-addressed, pre-stamped envelope. Receipt on our end is the start of official consent, and official enrollment begins with first phone call (Week 0). While this process generally worked, it was inefficient. For one, mailing delays often meant a lag between the person expressing interest and when s/he was officially enrolled. Second, there are occasional instances where the person does not fully complete the consent form (e.g., missing date), or does not return all necessary pages, and the process repeats itself (back and forth mailing) until we get all forms in full. Third, a large number (~55%) of the consent forms go un-returned, for any number of reasons. Thus, if we want a minimum of 648 participants, we would need to identify ~1180 who would be eligible and interested. Loss of interest in the study is a possibility (which we abide by), but we also believe that consents get lost, thrown away, regarded as junk mail (particularly if seen by someone else), etc. For the current study, we will continue with this procedure of mail-based consenting and add a new teleconsent process that addresses this inefficiency. After the initial determination of study eligibility, assessed online in our secure survey, participants will be asked about their capacity for teleconsent procedures, including access to a device and internet on which they can complete remote consent. For those who have the required hardware and software for teleconsent, we will then describe the basic mechanics of online consent process and ask for their preference for mode of consent: to be consented online or to receive a mailed consent. Participants can choose their preferred method of consent, and none of this is an eligibility requirement. Participants who do not meet teleconsent requirements will be mailed a consent form following standard procedures. Thus, we are simply offering another, more immediate option for study consent that may be preferable for some participants.

For those who elect teleconsent, we will follow IRB-approved procedures as per precedent. Participants who elect to complete the consent process online using doxy.me or REDCap will be consented by IRB-approved study personnel: the PI, study coordinator, or research assistants. All doxy.me signed consent forms will be saved as .pdf files within our study records and all REDCap documents are immediately saved in REDCap. Most of our ongoing studies employ this method, and a growing number of participants prefer this route of consent (currently ~55%). For those opting to receive consent packet through the mail, we will follow our prior procedures described above. Once they have received the consent form in the mail, we will have a scheduled phone call to discuss the consent and study with them. They will have the opportunity to ask any questions at this time, and participants cannot be enrolled without completing the phone discussion step of the consenting process. This phone call was added to our prior mailed consent procedures to ensure that participants have a full understanding of the consent form before enrolling in the study, as they would in person or with online consent.

We have a toll-free phone line to support anyone who calls with questions. Upon return to our office, data are entered into our database, and these individuals comprise the consented sample. However, the sample is reduced further to those with whom we are able to establish first phone contact (Day 0); i.e., the enrolled sample. This enrolled sample is the intent-to-treat sample.

[figure not shown]
Pre-Randomization Verification of Non-Pregnancy: For females age  $\leq 55$ , we impose one additional step to verify pregnancy status. We will mail these participants a commercially available pregnancy test to verify non-pregnancy status. We will then require these participants to confirm in writing via REDCap that they have completed the pregnancy test and have received a negative result. Participants are also informed that they should let us know if they become pregnant during the trial. Medications will not be sent until this verification is in place. These methods are IRB approved (and required) for our proof-of-concept pilot study.

Pre-Randomization Physician Approval for Medications: Finally, prior to study randomization, our study physician will review a summary of eligibility criteria, collected during Primary (e.g., smoking history, age, medical history and comorbidities) and Secondary screening (psychiatric history, suicidal history, pregnancy status) steps before the participant can be randomized and be enrolled into our trial. We will deliver this summary with a report that we create within our REDCap screening database, to be delivered electronically to the study physician. He will review each individual's information, and will make a determination to: 1) accept the individual into the study, 2) reject the individual into the study (i.e., not eligible for varenicline), or 3) ascertain more information from the individual before either of the decision to accept/reject the participant. In the latter, the study physician may contact the individual to engage in further clinical interview. The disposition of each participant will be tracked within this screening database, allowing us to complete all CONSORT steps to study flow. The individual will not proceed to randomization and Week 0 baseline call until we have signed, explicit documentation from the study physician to do so. This step for pre-randomization physician approval will sequentially follow the pregnancy test evaluation, since the former depends on the latter. Any individuals removed through either pregnancy test (test positive or non-responsive) or through physician discretion will not be counted in the final enrolled study sample. A summary of the overall study flow is depicted in the figure below (following page).

Thus, this procedure ensures that we retain physician oversight and approval of varenicline disbursement at study outset. Our study physician retains his role in evaluation of adverse events as noted elsewhere within this application.

While the source of varenicline within our trial is not yet clear, we will work with a TBD pharmacy to package and label varenicline. Both packaging and labelling will be done within TBD pharmacy, following all applicable laws. Under no circumstances will non-credentialed study staff package or label the medication. The TBD pharmacy will package and label the varenicline under our prescriber's order.

**Figure of Study Flow for STARS**

Randomization, Stratification We recruit smokers wanting to quit ( $\geq 7$  on 0-10 scale) and not, and we use this as a stratification variable. We considered a number of other stratification variables (e.g. cigs/day, insurance status) but believe that randomization will adequately handle these. We will randomize participants to group in a 2:1:1 ratio, with intent to increase precision of our parameter estimates within the varenicline group (n=324), consistent with our intent to understand use patterns and uptake of varenicline.

### *IIId Interventions and procedures*

All smokers in all groups will receive a mailing consisting of standard cessation support materials and specific contact information and benefits of using South Carolina quitline. Quitline benefits will convey the option, for some smokers, to receive free medication. Varenicline participants will receive one-time supply of medication in childproof pill bottle. In our prior sampling studies, we have been largely non-directive of medication use, simply suggesting to participants that they might use it in any number of ways, including not at all. This messaging was consistent with our naturalistic intent, i.e. to allow smokers to self-determine if and how to try the product. For a study of varenicline sampling, we aim to retain naturalistic context but may need to be more directive, including guidance on titration (see dosage comments below). Thus, our messaging will state ~ “*We are offering you a up to a four-week supply of varenicline, which we hope you find helpful. Evidence shows that varenicline is among the best medications to help smokers quit. It is also helpful for smokers who are not yet ready to quit. It is completely up to you if and how you take this. If you decide to try varenicline, start with taking one pill each day for 3 days, followed by a pill in the morning and a pill in the evening thereafter. If you want a stronger dose of medicine to help you quit, you may also go up to two pills in the morning and two pills in the evening after a week. If you ever take a day off and want to re-start, just start this process over again.*” This messaging was drafted and refined by four clinicians and is working well in our pilot study above. This messaging will be conveyed directly during intervention call and also within mailing (with accompanying calendar graphics to facilitate understanding). Both the phone-based and mailing messaging of varenicline sampling will suggest options for continued use beyond the sampling period and will be tailored to individual insurance status. As noted above, study eligibility is restricted to smokers who have access to a medical prescriber who can “convert” interested smokers into more sustained varenicline use. Our mailing will also include a generic letter that smokers can give to their provider stating that they have been pre-screened for and have received varenicline and should be considered for further use upon provider approval. It will be up to the participant to decide if and when to offer this letter to their individual provider. We cannot ensure that this conversion will be seamless, i.e., to occur immediately at the end of sampling period. The extent and timing of conversion is one study outcome.

We extensively debated varenicline dosing and sampling duration. Typical practice is to titrate as follows: .5mg QD for days 1-3, .5mg BID for days 4-7, and 1mg BID from day 8 and beyond. On one hand, we want to provide the strongest, most evidence-based dosage possible. If varenicline sampling results in null effect, we do not want this to be due to dosing. On the other hand, providing multiple dosages within a self-paced sampling experience could add unwanted confusion and risk. We are also aware of two large trials that showed similar outcomes of 1mg vs. 2mg dosing, with fewer adverse events in the former.(66, 67) To balance these perspectives, we: a) provide .5mg tablets only, 60 total, b) with instructions to titrate as noted within *italicized instructions* above, c) give instructions to take no more than two in the morning and two in the evening, d) give the participant the ultimate choice to self-pace usage. This choice and pattern of titration becomes an interesting study outcome that aligns with our focus on participant uptake and is wholly consistent with our naturalistic intent. Thus, we view the sampling experience as lasting 2-4 weeks depending on participant choice. For anyone who might ignore the titration schedule and start/restart with 2mg, nausea is the most likely consequence, nothing worse.

Smokers in the NRT group will follow our prior protocol: 4-week supply of both nicotine patch (14mg) and lozenge (4mg), with *comparable instructions for self-determined use as above*. As in our prior trials, we provide both patch and lozenge given different mechanisms of action (slow, cumulative dosing of patch vs. acute delivery for momentary craving with lozenges), and also because of strong evidence to show that superiority of combo NRT over placebo and single NRT products (85-87). We neither explicitly advise nor discourage combined use. Thus, this is an opportunity for smokers to learn about two NRT products, to be used individually or together (participant choice, including none at all). We will caution all participants on signs of receiving too much nicotine (nausea, dizziness) and will monitor adverse events, expected to be rare/mild.

### *IIIf Follow-Up Procedures*

Follow-up assessments will be auto-sent to participants at +17 days (2 weeks beyond initial mailing, accounting for ~ 3 day delay in mailing), +33 days (same delay), +2, +3 and +6 months. Participants are reimbursed for completion of each of five interviews at an escalating rate and with bonus for completion of all. We have excellent

history of participant retention across our prior studies. Spanning at least 5 trials, encompassing >10,000 participant phone contacts, we consistently complete 80-90%. In our prior study of NRT sampling in South Carolina, we completed 96% of all scheduled contacts, our best yet. Payments are sent after each completed assessment (gift card or code for online purchase), and again the procedures are well established. Participants will also be able to earn referral bonuses for referring friends and family who enroll in the study.

### *III f Assessments*

All interview data are entered in real time within a REDCap database, ensuring high data quality. We have established assessment protocols for all outcomes. Our follow-up interview has been extensively used in our prior studies and is timed at ~20 minutes. Self-report data include the following:

Baseline questionnaire will ascertain basic demographics and smoking history, including measures of dependence,(88) prior use of medications, and all hypothesized mediators (\*listed below).

Smoking (Reduction) Using Timeline Follow Back (TLFB) methods, we assess cigarettes per day over the previous seven days, and from this can calculate abstinence (defined below), as well as smoking reduction, and percent who achieve 50% reduction. We also track use of other tobacco products, including e-cigarettes.

Abstinence is defined as both “floating” (any 7 day period of non-smoking) and point prevalence, as recommended for “cessation-induction” studies.(89) We will track longest duration of abstinence and relapse following stated quit attempts.

Quit Attempts We will track the incidence of any self-defined and “serious” quit attempts over the 3-month follow-up period. The latter is the typical measure of quit attempts, used in CDC reports, and is defined as an attempt lasting  $\geq 24$ hrs. We will also report on the maximum duration, and latency of each QA since baseline.

Use of varenicline, NRT other meds We will determine the incidence and frequency of medications used, both during the sampling period and beyond. For varenicline, we will assess actual dosage used as well as titration patterns, days of use, and whether or not the person “converted” to sustained use (when, how, through whom).

\*Self-Efficacy, Motivation, & Confidence to Quit We will use single item (0-10 visual analog scale) measures for each. Our ladders have adequate test-retest stability and predictive validity.(90)

\*Attitudes Towards varenicline, NRT Based largely on prior work in this area(58, 91), we have published(25, 75) on 1) positive, and 2) negative attitudes towards medications, as well as 3) general knowledge of them.

\*Treatment Self-Regulation Questionnaire The TSRQ(47) is a well-established measure of autonomous motivation; i.e., the degree to which decisions on quitting are self-determined and/or controlled by others.

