### *III g Electronic Diaries during Sampling*

All participants will be asked to complete a brief diary to assess smoking behavior and use of meds. These diaries, which will include brief mood assessments, provide additional, real-time risk monitoring, not to replace traditional adverse event assessment (above), but to complement. Our intent is to better capture day-to-day fluctuations in medication use and smoking. Each of our recent trials have used this diary approach, with excellent compliance (88% for one study, 83% for another). Diaries will assess cigarettes smoked per day, medications/products used, purposes of that use (to reduce/quit), and mood/affect. Diaries ( $\leq 2$  min each) will be electronically collected daily throughout the sampling period (28 days). We have established procedures to auto-send an email/text on a set schedule. Thus, per eligibility criteria above, we require participants to have smartphone capacity, and they will be compensated for compliance based on % diaries completed (e.g., \$100 for 90-100% compliance, \$70 for 75-90% compliance, etc.). There is some debate as to whether EMA/diary procedures alter behavior, but recent evidence suggests not,(95, 96) but even if so this is equal between groups.

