Missing Data & Dropout: The most conservative approach for handling missing data(100) is to substitute them with baseline values, assuming outcomes have all returned to baseline, with no quit attempts made or abstinence achieved. If this assumption is incorrect, it biases the results towards the null by reducing between group differences.(100) We expect few missing data and thus plan for this approach. If missing data >10%, we will calculate results using this conservative method but also using methods in which missing data are imputed as described in the SRNT guidelines, and will assess whether dropout differs by study group (not the case in our prior trials). Abstinence will be reported both with and without (missing samples) CO verification.

Feasibility and Measures of Uptake: Our ongoing proof-of-concept study provides an early sense of study feasibility and thus this is not a main outcome of the trial. Nonetheless, we will deem our approach feasible if: a) at least 80% of varenicline group tries the medication, b) with reasonable duration of use (e.g., median days of use  $\geq 14$  days), c) at least 50% of varenicline group self-titrates to 2mg, d) at least 30% convert to independent use, and e) <5% of adverse events from varenicline are serious.

Binary Outcomes (incidence rate of quit attempts & cessation; % treatment uptake/conversion) will first be examined over the entire study period from baseline to end of follow-up by calculating frequencies/percentages as well as 95% confidence intervals for each medication group. Chi-square tests (or Fisher's exact tests as needed) will compare groups on binary outcomes to determine if effects from sampling group exceed those from control group. Both the control group (primary/powerful comparison) and NRT group (secondary) will serve as referent for varenicline group outcomes. Covariates will be included where necessary based on baseline differences. All tests will be considered significant at the  $\alpha=0.05$  level of significance.

Continuous Outcomes (duration of abstinence, smoking reduction) measured over the entire study period from baseline to the end of follow-up will be evaluated using general linear modeling with a main effect of group to determine group differences. Covariates will be added as necessary to account for baseline group differences.

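### After the diary month, a 7-day recall at the remaining follow-ups cannot by itself show floating abstinence or longest abstinent duration: most smoke-free spells of up to about four weeks would go unseen

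*Combined protocol and SAP*

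**What the plan says.** In section III f (Assessments), the smoking paragraph states the recall period and the derivation together: "we assess cigarettes per day over the previous seven days, and from this can calculate abstinence (defined below". The next paragraph gives the definition: "Abstinence is defined as both “floating” (any 7 day period of non-smoking) and point prevalence". It adds that this is the recommended approach for cessation-induction studies, and that longest abstinence, and relapse after stated quit attempts, will be tracked. The quit-attempt paragraph promises maximum duration and latency of each attempt since baseline, but sets the incidence of attempts over a three-month follow-up.

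The schedule is in section IIIf (Follow-Up Procedures): "Follow-up assessments will be auto-sent to participants at +17 days", then at "33 days (same delay), +2, +3 and +6 months", five surveys in all ("Participants are reimbursed for completion of each of five interviews"). The Specific Aims say the trial "will follow all for 6 months". Section III g adds diaries for all participants, recording cigarettes per day and "electronically collected daily throughout the sampling period (28 days". In section IIIi, the continuous outcomes are "duration of abstinence, smoking reduction) measured over the entire study period from baseline to the end of follow-up".

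**The concern.** A 7-day look-back shows a 7-day smoke-free run only when all seven look-back days are smoke-free. It is therefore the right instrument for point prevalence at a visit. It is the wrong one for an outcome defined as any smoke-free week, because the windows do not join up once the diaries stop. Short spells between the later visits leave no trace in the cigarette counts.

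Two reported results are at stake. Floating abstinence and longest duration would be undercounted from about the second month on, which is when participants may have moved to medication obtained independently. And smoking reduction described as covering the whole study would, after the first month, rest on three separate weeks.

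**Working it through.** The documents give no coverage figure, so there is none to reproduce. The check is a count of days.

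**Inputs.** Recall is 7 days (III f). Follow-ups are at days 17 and 33 and months 2, 3 and 6 (IIIf). Diaries run 28 days (III g). Assumptions: months fall at days 61, 91 and 183; diaries cover days 1–28; all surveys and diaries are completed.

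**Coverage.** The TLFB windows are days 11–17, 27–33, 55–61, 85–91 and 177–183.
- TLFB alone: 5 × 7 = 35 days; 35/183 = 19%.
- With diaries: days 1–33 are continuous, so 33 + 3 × 7 = 54 days; 54/183 = 30%.
- Remaining gaps: days 34–54 (21 days), 62–84 (23) and 92–176 (85).
- Between the month-3 and month-6 surveys: 7 of 92 days have a count, so about 92% have none.

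With months at days 60, 90 and 180, or diaries starting on day 4 to allow for mailing, the combined cover is 51–54 days, and 70–72% of the period has no daily count.

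**Detection of one spell starting after day 33.** A spell of length L starting on day s contains the window from day a to day a + 6 when a + 7 − L ≤ s ≤ a. Each start day is taken as equally likely. Two ranges of start day are used:
- A: the spell ends by day 183, so starts run from 34 to 184 − L, which is 151 − L days.
- B: the spell may still be running at day 183, so starts run from 34 to 177, which is 144 days.

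Start days that reveal the spell, by window (55–61, 85–91, 177–183):
- L = 14: 48–55 (8 days), 78–85 (8), and 170 only under A (1) or 170–177 under B (8).
- L = 30: 34–55 (22), 62–85 (24), and 154 only under A (1) or 154–177 under B (24).
- L = 60: the first two windows overlap and together give 34–85 (52); then 124 only under A (1) or 124–177 under B (54).

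| Spell length | A: ended by day 183 | B: may run past day 183 |
|---|---|---|
| 14 days | 17/137 = 12% | 24/144 = 17% |
| 30 days | 47/121 = 39% | 70/144 = 49% |
| 60 days | 53/91 = 58% | 106/144 = 74% |

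**Sensitivity.** With diaries on days 4–31, starts from day 32 and spells ended by the last day, detection is 2% at 7 days, 12% at 14, 36–37% at 28, 50% at 42, 57% at 56 and 81–83% at 85. If starts are spread over the whole six months, so that the diary month counts too, detection is 15–16% at 7 days, 26% at 14, 46–47% at 28, 61% at 42 and 87–89% at 85.

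**The case against.** The strongest reply is that the TLFB is not the only source. The diaries leave no gap in the first 33 days, so floating abstinence does not reduce to being point-prevalent at one of five visits. Section III f also plans to track longest abstinence and the duration and latency of each quit attempt, and latency plus duration can date a spell between visits. The tie to stated attempts may apply only to relapse. The text does not say abstinence comes only from the TLFB. The questionnaire is not in the documents, and section III f says established protocols exist for all outcomes. The team has reported floating abstinence before (Preliminary Studies, NRT Sampling Study 1).

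Much of this stands. A reader might infer that most abstinent spells between visits are missed altogether. The documents do not support that: they give no distribution of spell lengths, longer spells are mostly caught even on counts alone, and the quit-attempt items will catch others.

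It does not remove the point. Section III f does not assign floating abstinence to the quit-attempt items. Those items depend at least partly on the participant calling the spell an attempt, in a trial that deliberately enrols smokers who do not want to quit. Quit-attempt incidence is written for three months, so on a literal reading that route stops where the 85-day gap begins.

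On smoking reduction, the reply is largely right. Reduction is a level, and 7-day counts at each visit estimate it properly at those visits. What they do not support is a description of it as measured throughout.

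**Conclusion.** The point holds in a limited form. As written, the derivation of abstinence from 7-day counts cannot deliver any smoke-free week, or longest duration, after about day 33. Daily counts cover about 30% of six months with complete diaries and 19% without. Among spells that start after the diary period, the counts miss most of those lasting up to about four weeks; around six weeks, half or more are detected. Quit-attempt reports narrow the shortfall by an amount the documents do not let one estimate.

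These figures assume one spell per person, a uniform start day, months of 30 to 30.5 days and full compliance. Incomplete diaries or surveys would lower detection.

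A reader might also infer bias between arms or a threat to the main result. Neither follows. The schedule is the same in every arm, and no differential effect has been shown. Six-month point prevalence, on which section IIIi bases the sample size, is measured directly by the last 7-day window.

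**What to change.** Keep the 7-day TLFB for point prevalence and for smoking reduction, with reduction reported at each visit. At every follow-up to month 6, in all arms, add a short item worded independently of quit attempts: since the last completed survey, was there any run of 7 or more days without smoking, when did it start, and how long was the longest run? Derive floating abstinence and longest duration from that item plus the diaries, and say so in sections III f and IIIi. Reconcile the three-month quit-attempt period with the six-month follow-up.

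The cost is a few survey items, 1–3 minutes per follow-up, and recall of about three months at the month-6 survey (longer if a survey was missed).

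If data collection is too far advanced to add an item, change the wording instead. Define floating abstinence as observed only within the diary and TLFB windows, and do not describe it or smoking reduction as covering the entire study period.
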